**Duration of Treatment and Follow-up:**

Patients will receive study treatment for up to 14 days.

Dosing can continue for an additional 2 weeks if ANY of the following criteria are met:

1. Patients who remain hospitalized must meet the following criteria to continue selinexor therapy:
  - a. has not had a selinexor-related Grade 4 Adverse Event (AE) or selinexor-related Serious AE (SAE) AND
  - b. has not had >1 point ordinal score reduction (worsening) OR
  - c. has 2 point reduction (worsening) in ordinal score with a  $\geq 20\%$  absolute reduction in FiO2 from peak oxygen requirement
2. Patients discharged from the hospital before Day 28 must meet the following criteria to continue selinexor therapy:
  - a. Platelet count > 75,000/mm^3 and
  - b. Neutrophil count >1,000/mm^3 and
  - c. Serum sodium > 130 mmol/L and
  - d. No Grade  $\geq 3$  nausea or vomiting and
  - e. No Grade 4 AEs related to selinexor, and
  - f. Improved ordinal score from baseline AND
  - g. Positive SARS-CoV2 by FDA approved laboratory test at discharge

Note: patients discharged from the hospital who remain on selinexor must continue to have twice weekly serum chemistry and complete blood counts as long as treatment is continued.

Therapy will be stopped if any of the events defined below occur prior to 28 days:

- Patient withdraws consent to continue study treatment.
- Worsening clinical condition defined as at least 5 days of intubation/ECMO with no evidence of clinical improvement. Patients who are clinically stable based on oxygen requirements on mechanical ventilation will be permitted to remain on study.
- Grade  $\geq 3$  nausea or vomiting despite optimal antiemetic therapy.
- Progression of renal dysfunction requiring dialysis.
- Grade 4 AEs related to selinexor

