| 
Overall Study Design:
 
This is a randomized phase 2 single-blinded study of low dose selinexor versus placebo to evaluate the activity and safety, as well as reduction in mortality in patients with severe COVID-19.
 
The study population will consist of hospitalized patients ≥18 years old with COVID-19.
 
The enrollment will be stratified by:
 
 
• Use of concomitant therapies: an anti-viral (e.g., remdesivir) or an anti-inflammatory (e.g. hydroxychloroquine, biologics targeting e.g., IL-6 or IL-1). Note: acetaminophen and nonsteroidal anti-inflammatory drugs (NSAIDs) will not constitute anti-inflammatory agents for the purposes of stratification.
 
• High Risk Comorbidities: Age > 75, BMI > 30, cancer patients on chemotherapy, patients with cardiac (CAD, AMI, CHF) or pulmonary (COPD, emphysema) disease diabetes, hypertension). Stratification will be based on number of high risk comorbidities: (1 vs ≥2 vs 0)
 
 
A dose of 20-mg selinexor or matching placebo will be administered orally on Days 1, 3, and 5 of each week for up to 2 weeks. If the patient is tolerating therapy and clinically benefitting (i.e., not meeting
 |   |

any of the criteria for stopping therapy listed below), dosing can continue for an additional 2 weeks (on Days 15, 17, 19, 22, 24, and 26).

Patients who achieve ANY of the following criteria will be considered as having clinical benefit for the purpose of continuing dosing for an additional 2 weeks.

1. Patients who remains hospitalized and:
  - a. Has not had a selinexor-related Grade 4 AE or selinexor-related serious AE (SAE)  
AND
  - b. Has not had >1 point ordinal score reduction (worsening)  
OR
  - c. Has 2 point reduction (worsening) in ordinal score with a  $\geq 20\%$  absolute reduction in FiO2 from peak oxygen requirement
2. Patients discharged from the hospital before Day 28 must meet the following criteria in order to continue on selinexor:
  - a. Platelet count  $>75,000/\text{mm}^3$  and
  - b. Neutrophil count  $>1,000/\text{mm}^3$  and
  - c. Serum sodium  $>130$  mmol/L and
  - d. No Grade  $\geq 3$  nausea or vomiting and
  - e. No Grade 4 AEs considered to be related to selinexor and
  - f. Improved ordinal score from baseline AND
  - g. Positive SARS-CoV2 by FDA approved laboratory test at discharge

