| CCI  |            |                                   |           |           |           |            |            |             |             |            |            |                  |                    |  |

|  |   |                     |   |   |   |   |                |     |     |     |     |   |  |   |
|--|---|---------------------|---|---|---|---|----------------|-----|-----|-----|-----|---|--|---|
| Cells for Leukocyte Phenotyping f             | X | X                   |   |   | X |   | X g | X   |     |     |     |   |  |   |
| Selinexor or Placebo k                        |   | X                   | X | X | X | X | X              | (X) | (X) | (X) | (X) |   |  |   |
| Blood draws for selinexor PK h                |   | X                   | X | X |   |   |                |     |     |     |     |   |  |   |
| Cytokines  | X |                     | X | X | X |   |                |     |     |     |     |   |  |   |
| Adverse Events (any)                                     | X | Recorded Throughout |   |   |   |   |                |     |     |     |     | X |  | X |
| Concomitant Medications                                  | X | Recorded Throughout |   |   |   |   |                |     |     |     |     | X |  |   |
| 5-HT3 antagonists Ondansetron or equivalent i |   | Daily as needed     |   |   |   |   |                |     |     |     |     |   |  |   |
| Survival Follow-up                                       |   |                     |   |   |   |   |                |     |     |     |     |   |  | X |

a Patients will remain on therapy for up to 14 days (or 28 days based on treating physician discretion)

b Refer to [Section 10.1](#) for Informed Consent

c Vital signs include respiratory rate, temperature, and oxygen saturation It is recommended to measure SpO2 in the same position for each patient throughout the duration of the study

d Ordinal Score ([Section 7.3.2](#)) will be assessed at first assessment of day

e For patients who had an ECG during the hospitalization, the ECG does not need to be repeated. Results of this most recent ECG should entered into the eCRF

f Required study and should be performed unless hospital SOP does not permit or if not feasible, to be performed locally as available. Once 2 negative viral assessments are documented testing can be stopped.

g Day 12 or Day 15

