### 3. STUDY DESIGN

#### 3.1. Overall Design

This is a randomized phase 2, single-blinded study of low dose selinexor versus placebo to evaluate the activity in patients with severe COVID-19.

The study has 2 arms and will evaluate selinexor 20 mg + standard of care (SoC) and placebo + SoC. As the treatment for COVID-19 is rapidly evolving, the SoC will vary over time and across regions of the world. Therefore, SoC may include antibiotics (e.g., azithromycin), anti-malarial (e.g., hydroxychloroquine), or antivirals (e.g., remdesivir), and other agents (e.g., anti-IL-6 antibodies) to be per the institution at each site. The randomization and stratification will minimize any influence in the variability of SoC.

The study population will consist of hospitalized patients  $\geq 18$  years old with COVID-19.

The enrollment will be stratified based on criteria in [Section 4.4](#):

Enrollment will be paused for evaluation of safety and efficacy after the enrollment of the first 40 patients and the first meeting of the DSMB will occur within the first week of enrolling the 40th patient. No further patients will be enrolled until the completion of this DSMB review and the safety and efficacy data from the first 40 patients will be shared with the FDA prior to resuming enrollment.

A dose of 20 mg selinexor or matching placebo will be administered orally on Days 1, 3, and 5 of each week for up to 2 weeks. If the patient is tolerating therapy and clinically benefitting (i.e., not meeting any of the criteria for stopping therapy listed below), dosing can continue for an additional 2 weeks (on Days 15, 17, 19, 22, 24, and 26). It is recommended that patients are dosed with study drug within 12 hours of providing consent.

Patients who achieve ANY of the following criteria will be considered as having clinical benefit for the purpose of continuing dosing for an additional 2 weeks.

1. Patient remains hospitalized and:
  - a. Has not had a selinexor-related Grade 4 AE or selinexor-related serious AE (SAE)  
AND
  - b. Has not had  $>1$  point ordinal score reduction (worsening)  
OR
  - c. Has 2 point reduction (worsening) in ordinal score with a  $\geq 20\%$  absolute reduction in  $\text{FiO}_2$  from peak oxygen requirement
2. Patients discharged from the hospital before Day 28 must meet the following criteria in order to continue on selinexor:
  - a. Platelet count  $>75,000/\text{mm}^3$  and
  - b. Neutrophil count  $>1,000/\text{mm}^3$  and

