## 5. STUDY TREATMENT

### 5.1. Study Treatment Administered

**Table 3: Study Treatment Administered**

|                                |   |
|--------------------------------|---|
| Treatment Name          | Selinexor (XPOVIO ® , KPT-330) / Placebo |
| Type                    | Drug  |
| Dose Formulation        | Tablet  |
| Unit Dose Strength      | 20 mg   |
| Dosage Level            | 20 mg, single dose                                  |
| Route of Administration | Oral  |

A dose of 20 mg selinexor or matching placebo will be administered orally on Days 1, 3, and 5 of each week for up to 2 weeks. If the patient is tolerating therapy and clinically benefitting (defined below), dosing can continue for an additional 2 weeks (on Days 15, 17, 19, 22, 24, and 26).

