**Table 5: Selinexor Dosage Modification for Adverse Reactions**

| Adverse Reaction a  | Occurrence | Action   |
|--|------------|--|
| Hematologic Adverse Reactions   |            |  |
| Thrombocytopenia  |            |  |
| Platelet count 25,000 to less than 50,000/mcL                                    | Any        | 
 
• Reduce selinexor by 1 dose level (see Table 4).
 
  |
| Platelet count 25,000 to less than 50,000/mcL with concurrent G3 bleeding | Any        | 
 
• Interrupt selinexor and provide appropriate supportive care.
 
• Restart selinexor after bleeding has resolved at 1 dose level lower (see Table 4).
 
   |
| Platelet count less than 25,000/mcL  | Any        | 
 
• Interrupt selinexor and provide appropriate supportive care.
 
• Monitor until platelet count returns to at least 50,000/mcL.
 
• Restart selinexor at 1 dose level lower (see Table 4).
 
   |
| Neutropenia   |            |  |
| Absolute neutrophil count of 0.5 to 1.0 x 10  /L with fever   | Any        | 
 
• Interrupt selinexor and provide appropriate supportive care.
 
• Monitor until neutrophil counts return to 1.0 x 10^9/L or higher.
 
• Restart selinexor at 1 dose level lower (see Table 4).
 
  |
| Absolute neutrophil count less than 0.5 x 10  /L                     | Any        | 
 
• Interrupt selinexor and provide appropriate supportive care.
 
• Monitor until neutrophil counts return to 1.0 x 10^9/L or higher.
 
• Restart selinexor at 1 dose level lower (see Table 4).
 
  |
| Anemia  |            |  |
| Hemoglobin less than 8.0 g/dL  | Any        | 
 
• Reduce selinexor by 1 dose level (see Table 4).
 
• Administer blood transfusions and/or other treatments per clinical guidelines.
 
  |

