| Grade 3 or higher (increase of 7 stools or more per day over baseline; hospitalization indicated)   | Any                            | 
 
Interrupt selinexor and institute supportive care.
 
Monitor until diarrhea resolves to Grade 2 or lower.
 
Restart selinexor at 1 dose level lower (see Table 4).
 
   |
| Weight Loss and Anorexia   |                                |  |
| Weight loss of 10% to less than 20%
OR anorexia associated with significant weight loss or malnutrition not due to intensive care status                        | Any                            | 
 
Interrupt selinexor and institute supportive care.
 
Monitor until weight returns to more than 90% of baseline weight.
 
Restart selinexor at 1 dose level lower (see Table 4).
 
  |
| Other Adverse Reactions  |                                |  |
| Grade 3 or 4 non-hematologic reactions  | Any                            | 
 
Interrupt selinexor.
 
Monitor until resolved to Grade 2 or lower, restart selinexor at 1 dose level lower (see Table 4).
 
   |
| Life-threatening hematological and non-hematological (Grade 4) AEs related to selinexor  | Any                            | 
 
Discontinue selinexor
 
  |

a National Cancer Institute Common Terminology Criteria for Adverse Events (NCI CTCAE) version 5.0. Only adverse reactions to selinexor should lead to dose adjustments.

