### **6.2. Patient Discontinuation/Withdrawal from the Study**

A patient may withdraw from the study at any time at his/her own request or may be withdrawn at any time at the discretion of the Investigator for safety, behavioral, compliance, or administrative reasons. Waivers for eligibility criteria for enrollment will not be permitted. The criteria given below are reasons the investigator must consider for removal of patients from study.

The Investigator must determine the primary reason for a patient's discontinuation of study treatment/withdrawal from the study and record this information on the electronic case report form (eCRF).

The Investigator may remove a patient from study treatment for any of the following reasons:

- Unacceptable AEs or toxicity that cannot be managed by supportive care
- Significant deviations from inclusion/exclusion criteria
- Missed / unscheduled / off-schedule / incomplete / incorrect assessments that result in patients being put at risk
- Any other medically appropriate reason or significant protocol violation, in the opinion of the Investigator.

The Investigator must remove a patient from study treatment for any of the following reasons:

- Patient withdraws consent to continue study treatment.
- Worsening clinical condition defined as at least 5 days of intubation/ECMO with no evidence of clinical improvement. Patients who are clinically stable based on oxygen requirements on mechanical ventilation will be permitted to remain on study.
- Grade  $\geq 3$  nausea or vomiting despite optimal antiemetic therapy.
- Progression of renal dysfunction requiring dialysis.
- Grade 4 AEs related to selinexor.

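### For patients still in hospital, the protocol's rules for dosing after Day 14 disagree: item 1 bars patients whom Table 1 note a and the i.e. clause would let continue

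*Protocol*

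**What the plan says.** Four pieces of current protocol text bear on who may be dosed after Day 14.

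- **Items 1 and 2** (Synopsis, Overall Study Design and Duration of Treatment and Follow-up; Section 3.1). For admitted patients the Synopsis says "Patients who remain hospitalized must meet the following criteria to continue selinexor therapy". Part a: no related Grade 4 event and no related serious event. Part b: no worsening of more than one ordinal point. Part c: a two-point worsening is acceptable if FiO2 has fallen by at least 20% absolute from its peak. The parts are joined as a AND b OR c. Item 2 lists seven conditions, 2a to 2g, for discharged patients, all required.
- **The i.e. clause** (Synopsis, Overall Study Design; Section 3.1): "If the patient is tolerating therapy and clinically benefitting (i.e., not meeting any of the criteria for stopping therapy listed below), dosing can continue". Shortly after it, the Synopsis adds: "Patients who achieve ANY of the following criteria will be considered as having clinical benefit for the purpose of continuing dosing".
- **Table 1 note a**, in the schedule for admitted patients: "Patients will remain on therapy for up to 14 days (or 28 days based on treating physician discretion".
- **Section 5.1**: "If the patient is tolerating therapy and clinically benefitting (defined below), dosing can continue for an additional 2 weeks". Section 5 contains no such definition.

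The stopping list is in the Synopsis (Duration of Treatment and Follow-up) and Section 6.2. It has five events: withdrawn consent; at least 5 days of intubation or ECMO without improvement; Grade 3 or higher nausea or vomiting despite optimal antiemetics; dialysis; and a related Grade 4 event. SAP Section 2.1 repeats the tolerating-and-benefitting condition without defining it.

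**The concern.** Item 1 is an entry gate; the stopping list is a set of exit events. They are different tests, yet the i.e. clause treats the absence of an exit event as sufficient for entry, and note a names no test at all. No text says which prevails.

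The difference falls on two groups of admitted patients: those who have had a related serious event below Grade 4, and those who have worsened by two points but have been intubated for less than 5 days. The first group is the one the safety condition in item 1a exists to protect. With about 40 sites planned, different sites could follow different texts in good faith. Week 3-4 exposure, and the adverse events attributed to it, would then depend partly on which paragraph was read.

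**Working it through.** There is no sample size, power or error rate to reproduce. The check is to apply each text to the same patient and then count doses.

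**Step 1: admitted patients.** Consider a patient in hospital after Day 14 with no stopping event.

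| Patient | Item 1 as a AND (b OR c) | Item 1 as (a AND b) OR c | i.e. clause | Note a |
|---|---|---|---|---|
| No related SAE; worsened by 0 or 1 point | allowed | allowed | allowed | physician |
| No related SAE; 2 points worse, FiO2 exception met | allowed | allowed | allowed | physician |
| No related SAE; 2 points worse, exception not met | **barred** | **barred** | allowed | physician |
| Related SAE below Grade 4; worsened by 0 or 1 point | **barred** | **barred** | allowed | physician |
| Related SAE below Grade 4; 2 points worse, exception met | **barred** | allowed | allowed | physician |
| Related SAE below Grade 4; 2 points worse, exception not met | **barred** | **barred** | allowed | physician |

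Written out as separate states (related SAE yes/no × worsening 0, 1 or 2 × FiO2 fall yes/no), there are 2 × 3 × 2 = 12 that the i.e. clause allows. Item 1 bars 1 + 4 + 1 = 6 of them under either grouping, and 1 more depends on the grouping. These are counts of logical states, not of patients.

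**Step 2: the grouping.** The two readings differ only when a fails and c holds. A related Grade 4 event stops treatment anyway, so the grouping matters only for related serious events below Grade 4.

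**Step 3: which worsening is involved.** Assume a baseline score of 3 or 4 and worsening counted from baseline. Two points down from 3 is death; two points down from 4 is score 2. Part b therefore fails, among survivors, only for patients who started at 4 and are now ventilated or on ECMO.

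**Step 4: discharged patients.** Compare item 2 with the stopping list.

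- 2a (platelets), 2b (neutrophils), 2c (sodium) and 2g (positive test at discharge) have no counterpart in the stopping list.
- 2d is stricter than its counterpart: it excludes any Grade 3 or higher nausea or vomiting, while the stopping event requires failure of optimal antiemetics.
- 2e repeats a stopping event.
- 2f is met by almost anyone discharged, since discharge means a score of 7 or 8.

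In practice the i.e. clause is looser on 2a to 2d and 2g.

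**Step 5: doses at issue.**

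- First course: Days 1, 3, 5, 8, 10, 12 = 6 doses × 20 mg = 120 mg.
- Extension: Days 15, 17, 19, 22, 24, 26 = 6 doses = 120 mg. Total 12 doses, 240 mg.
- At the reduced schedule (Days 1 and 3 weekly) the extension is Days 15, 17, 22, 24 = 4 doses × 20 mg = 80 mg.
- A patient intubated on Days 12 to 14 who does not improve reaches the 5-day stopping event after 1 or 2 extension doses.
- The 30-day treatment-emergent window closes on Day 12 + 30 = 42 without the extension, and on Day 26 + 30 = 56 with all of it.

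**The case against.** The best contrary case is that the operative rule can be identified. Item 1 is phrased as an obligation. The criteria list is expressly tied to clinical benefit, and in Section 3.1 it is the only list below the i.e. clause. Section 7 describes the schedule as a summary, so note a could be read as discretion exercised within item 1. Entry gate and stopping list would then apply together.

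That is a sensible reading and probably the intended one, but the text does not state it. The i.e. clause names criteria for stopping, and note a cites no criteria. Table 2 note c, for outpatients, does defer to the protocol's criteria; note a has no such link.

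It can also be said that the word tolerating would bar a patient with a related serious event. Read literally, the i.e. clause covers tolerating as well as benefitting. If it does not, tolerating is undefined. Either way note a is unaffected.

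Four stronger inferences are not supported.

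- **That discharged patients have no clear rule**, for example one sent home on Day 10 with a negative test. Item 2 is mandatory, 2g addresses exactly that patient, and Table 2 note c defers to the protocol's criteria.
- **That Section 6.2 positively entitles stable ventilated patients to further dosing** through "Patients who are clinically stable based on oxygen requirements on mechanical ventilation will be permitted to remain on study". Remaining on study need not mean remaining on drug; Section 6.1 separates the two. The case of intubation for under 5 days does not need that sentence.
- **That Table 5 contradicts item 1a** because it says "Monitor until resolved to Grade 2 or lower, restart selinexor at 1 dose level lower". Table 5 governs dose modification, not eligibility for the extension. It shows only that such an event does not by itself end treatment.
- **That the Table 5 platelet threshold**, "Monitor until platelet count returns to at least 50,000/mcL", contradicts the limit of more than 75,000 in 2a. A stricter limit for outpatients, who are monitored less closely, is coherent.

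**Conclusion.** The inconsistency is real for admitted patients and minor. Item 1 bars two groups whom the i.e. clause allows and whom note a leaves to the physician: patients with a related serious event below Grade 4, and patients two points worse, outside the FiO2 exception, with under 5 days of intubation or ECMO. The ungrouped AND/OR is a separate defect that can let part c override the related-SAE bar. For discharged patients only the i.e. clause is out of line with an otherwise clear rule.

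Up to 6 doses (120 mg) per patient are at stake, or 4 doses (80 mg) at the reduced schedule. How many patients would be affected cannot be estimated from the documents. Step 3 rests on a baseline score of 3 or 4 and on worsening being measured from baseline.

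A reader might infer that the main efficacy result is compromised. It is not: the primary endpoint is read at Day 14, before any extension dose, and the same rules apply to both blinded arms. What suffers is the consistency of week 3-4 exposure and the safety data that follow from it.

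**What to change.** Three wording edits.

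1. In the Synopsis (Overall Study Design) and Section 3.1, replace the i.e. clause with: *meeting criterion 1 or 2 below and no stopping criterion in Section 6.2*. In Section 5.1, point the definition to Section 3.1.
2. In Table 1 note a, replace the discretion wording with: *if criterion 1 in Section 3.1 is met; the physician may decide not to continue*. Discretion can then withhold the extension but cannot waive the gate.
3. Write item 1 as *a AND (b OR c)* wherever it appears (both Synopsis sections and Section 3.1), so that part c cannot admit a patient with a related serious event.

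The cost is a wording amendment, with no new visits, procedures or patients. New timing rules for checking item 2 would be a change of policy and are not needed to resolve this point.

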**Study Treatment/Treatment Groups, Dose, and Mode of Administration:**

A dose of 20 mg selinexor or matching placebo will be administered orally on Days 1, 3, and 5 of each week for up to 2 weeks. If the patient is tolerating therapy and clinically benefitting, as defined below, dosing can continue for an additional 2 weeks (on Days 15, 17, 19, 22, 24, and 26).

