  - c. Serum sodium  $>130$  mmol/L and
  - d. No Grade  $\geq 3$  nausea or vomiting and

- e. No Grade 4 AEs considered to be related to selinexor and
- f. Improved ordinal score from baseline and
- g. Positive SARS-CoV2 by FDA approved laboratory test at discharge

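### A selinexor-related SAE below Grade 4 bars the Day 15-28 extension for patients still in hospital but not for discharged patients

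*Protocol*

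**What the plan says.** The extension criteria appear three times in the protocol: Synopsis, Overall Study Design; Synopsis, Duration of Treatment and Follow-up; and Section 3.1. The SAP (Section 2.1) mentions the extension but sets no criteria of its own.

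**Patients still in hospital (clause 1).** Item 1a reads "has not had a selinexor-related Grade 4 Adverse Event (AE) or selinexor-related Serious AE (SAE) AND" in the Duration section, and "Has not had a selinexor-related Grade 4 AE or selinexor-related serious AE (SAE") in the Overall Study Design part of the synopsis. Item 1b follows: "has not had >1 point ordinal score reduction (worsening) OR". Item 1c then admits a 2-point worsening if FiO2 has come down by at least 20% absolute from its peak. No brackets show how the AND and the OR group.

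**Patients discharged before Day 28 (clause 2).** Items 2a-2c set limits for platelets, neutrophils and sodium, and 2d excludes Grade 3 or higher nausea or vomiting. Item 2e is "No Grade 4 AEs related to selinexor, and" in the synopsis and "No Grade 4 AEs considered to be related to selinexor and" in Section 3.1. Items 2f and 2g require an improved ordinal score and a positive test at discharge. Related SAEs are not mentioned.

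**Stopping rules.** The synopsis list and the mandatory list in Section 6.2 have the same five items: withdrawn consent, prolonged intubation or ECMO without improvement, refractory Grade 3 or higher nausea or vomiting, dialysis, and related Grade 4 AEs.

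**The concern.** Both clauses decide whether a patient may enter the same optional two weeks of dosing. A history of a drug-related serious event bears on that decision wherever the patient is, yet only the inpatient clause asks about it. Followed literally, the plan withholds further selinexor from a patient under daily observation and allows it, after the same event, for a patient at home who is contacted weekly. Sites could also apply the rule differently. At stake are participant safety and consistent conduct during the extension, not the inference on the primary endpoint.

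**Working it through.** The protocol gives no figure to reproduce. The check follows one event through every rule, then looks at the logic, timing and size.

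**1. One event through the rules.** Take a related Grade 3 diarrhoea that lengthens the hospital stay and then resolves. Section 8.1.1 counts a lengthened stay as serious, so this is a related SAE below Grade 4.

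| Rule | Effect on the extension |
|---|---|
| Clause 1a (inpatient) | Barred |
| 2a-2c (discharged) | Not barred: current laboratory values only |
| 2d | Not barred: nausea and vomiting only |
| 2e | Not barred: Grade 4 only |
| 2f, 2g | Not barred: ordinal score and viral test |
| Synopsis stopping list; Section 6.2 mandatory list | Not barred: related Grade 4 AEs, not related SAEs |
| Section 5.7 text | Not barred: related Grade 4 only |
| Table 5 | Interrupt, then restart one level lower once the event is Grade 2 or lower |
| Section 6.2 permissive list | Removal for unacceptable toxicity is possible, at the investigator's discretion |

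Only 1a bars the patient, and it applies only in hospital.

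**2. Logic of clause 1.** With a related SAE, a is false.
- Read as a AND (b OR c), the result is always false.
- Read as (a AND b) OR c, the result equals c.

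Across 4 levels of worsening (0, 1, 2, 3 points) x FiO2 reduction yes or no = 8 combinations, the first reading passes 0. The second passes 1: exactly 2 points of worsening with the FiO2 reduction. Under that reading 1c bypasses the SAE bar. In clause 2 a related SAE is not a term at all, so any patient who meets 2a-2g passes.

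**3. Timing.** Clause 2 applies to discharge at any time before Day 28. A patient barred under 1a on Day 15 and discharged on Day 20 could then qualify for the doses on Days 22, 24 and 26 (3 x 20 = 60 mg). The clause speaks of continuing treatment, which points the other way, but nothing in it refers back to a failed clause 1.

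**4. Dose at stake.**
- Full extension: Days 15, 17, 19, 22, 24, 26 = 6 x 20 = 120 mg.
- Table 4 reduced level: 2 doses x 2 weeks x 20 = 80 mg.

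**5. Observation, Days 15-28 (Tables 1 and 2).**
- In hospital: vital signs twice daily, 2 x 14 = 28 sets, and 14 daily ordinal scores.
- After discharge: 2 weekly calls with AE collection, plus an ordinal score the day after discharge.
- Laboratory draws: 4 in each setting (Days 15, 19, 22, 26 in hospital; 2 x 2 at home).

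The outpatient tally may be incomplete. Table 2 has a redacted row and refers to a sponsor risk-management plan that is not available here.

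**6. Number of patients.** The documents give no rate of related SAEs. The selinexor arm has about 247/2 = 123.5 patients, or 50 x 2/3 + 197/2 = 131.8 if the first 50 were allocated 2:1 (SAP 7.1.1). Purely as an assumption, if 1% to 3% of them had such an event and met 2a-2g, that is 1.2-1.3 to 3.7-4.0, or roughly 1 to 4 patients.

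**The case against.** The strongest reply is that 1a is the outlier, not 2e. Elsewhere the protocol discontinues for related Grade 4 AEs and lets patients restart at a lower level after Grade 3 reactions. Clause 2 is also stricter in other respects, so different rules by setting could be intended. That is possible, but no reason is stated. Table 5 governs an event during treatment and does not explain why entry to optional dosing should depend on setting. It is also fair to say that the proposed change leaves an SAE first occurring after Day 15 to Table 5. That is already so for inpatients.

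The gap is narrow, and this part of the objection stands. Life-threatening events are Grade 4 and already excluded. Relatedness is strictly defined (Section 8.1.3). The patient must also have improved, test positive, pass the laboratory limits and be tolerating therapy. Sections 6.2, 7, 7.3.4 and 10.5 add discretionary removal, prompt discussion of safety concerns with the sponsor, laboratory review before dosing, and DSMB review of SAEs.

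A reader might go further and infer that eligibility is undetermined because the protocol defines clinical benefit twice. Section 3.1 says "clinically benefitting (i.e., not meeting any of the criteria for stopping therapy listed below), dosing can continue for an additional 2 weeks" and then gives the list, whereas the treatment part of the synopsis says "If the patient is tolerating therapy and clinically benefitting, as defined below, dosing can continue for an additional 2 weeks". Taken alone, the two tests do differ: the parenthesis omits related SAEs, and the list omits items such as "Worsening clinical condition defined as at least 5 days of intubation/ECMO with no evidence of clinical improvement". The documents do not support the stronger reading. The Duration section makes the list mandatory for inpatients, and the stopping rules bind regardless. Together they give one rule: meet the list and meet no stopping criterion.

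**Conclusion.** The point holds as a minor inconsistency. A selinexor-related SAE below Grade 4 bars extension in hospital and not after discharge, without a stated reason, and no other mandatory rule supplies the bar. The missing brackets in clause 1 add a second, narrower route past it.

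The number affected is unknown and probably small. The 1 to 4 patients above rest wholly on an assumed 1% to 3%. The dose at stake is 80 to 120 mg for a full extension, and less after a later discharge.

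Two further inferences should be resisted. The trial's main result is not threatened: extension dosing starts on Day 15, so the Day 14 endpoint, the sample size and the error rate are untouched, and with patients and site investigators blinded no directional bias is expected. Nor are discharged patients left unmonitored: scheduled laboratory draws are as frequent as in hospital. Clinical contact is what becomes sparser.

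**What to change.** 1. Add 'no selinexor-related SAE' to clause 2 in the Synopsis (Overall Study Design; Duration of Treatment and Follow-up) and in Section 3.1.
2. Write clause 1 as a AND (b OR c) in the same three places.

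This is a wording amendment with no extra patients, visits or procedures. The downside is that a few discharged patients with a related SAE lose the optional extension. If the sponsor does intend a different rule by setting, the protocol should state the reason. No new stopping rule for Days 15-28 is proposed, and Table 5 stays as it is.

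Optional editorial clean-ups in the same amendment:
- replace the parenthesis in the Synopsis (Overall Study Design) and Section 3.1 with the combined rule (list met and no stopping criterion met);
- point Section 5.1 to Section 3.1, since no definition follows in Section 5;
- make Table 1 footnote a refer to the protocol criteria, as Table 2 footnote c does, rather than to physician discretion alone.
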